8.4 SAFETY AND OTHER ASSESSMENTS

8.4.1 ADVERSE EVENT DEFINITIONS

Adverse Event: Any untoward medical occurrence in a human subject, including any abnormal sign (e.g., abnormal physical exam or laboratory finding), symptom, or disease, temporally associated with the subject's participation in the research, whether or not considered related to the subject's participation in the research.

Serious Adverse Event: Any AE that

- results in death;
- is life-threatening (places the subject at immediate risk of death from the event as it occurred);
- results in inpatient hospitalization or prolongation of existing hospitalization;
- results in a persistent or significant disability/incapacity;
- results in a congenital anomaly/birth defect; or
- based upon appropriate medical judgment, may jeopardize the subject's health and may require medical or surgical intervention to prevent one of the other outcomes listed in this definition (examples of such events include allergic bronchospasm requiring intensive treatment in the emergency room or at home, blood dyscrasias or convulsions that do not result in inpatient hospitalization, or the development of drug dependency or drug abuse).

Unanticipated Problem Involving Risks to Subjects or Others (UP): Any incident, experience, or outcome that meets all of the following criteria:

1. **Unexpected** (in terms of nature, severity, or frequency) given
 - a. the research procedures that are described in protocol-related documents, such as the IRB-approved research protocol and informed consent document; and
 - b. the characteristics of the subject population being studied; and
2. **Related or possibly related** to participation in the research (possibly related means there is a reasonable possibility that the incident, experience, or outcome may have been caused by the procedures involved in the research); and
3. Suggests that the research places subjects or others (which may include research staff, family members, or other individuals not directly participating in the research) at a **greater risk of harm** (including physical, psychological, economic, or social harm) related to the research than was previously known or expected.

Protocol Deviation: Any change, divergence, or departure from the IRB approved research protocol.

- **Major Deviations:** Deviations from the IRB-approved protocol that have or may have the potential to negatively impact the rights, welfare, or safety of the subject, or to substantially negatively impact the scientific integrity or validity of the study.
- **Minor Deviations:** Deviations that do not have the potential to negatively impact the rights, safety, or welfare of subjects or others, or the scientific integrity or validity of the study.

Non-compliance: Failure of investigator(s) to follow the applicable laws, regulations, or institutional policies governing the protection of human subjects in research, or the requirements or determinations of the IRB, whether intentional or not.

- **Serious non-compliance:** Non-compliance, whether intentional or not, that results in harm or otherwise materially compromises the rights, welfare and/or safety of the subject.

Non-compliance that materially affects the scientific integrity or validity of the research may be considered serious non-compliance, even if it does not result in direct harm to research subjects.

- *Continuing non-compliance:* A pattern of recurring non-compliance that either has resulted, or, if continued, may result in harm to subjects or otherwise materially compromise the rights, welfare and/or safety of subjects, affect the scientific integrity of the study or validity of the results. The pattern may comprise repetition of the same non-compliant action(s), or different noncompliant events. Such non-compliance may be unintentional (e.g., due to lack of understanding, knowledge, or commitment), or intentional (e.g., due to deliberate choice to ignore or compromise the requirements of any applicable regulation, organizational policy, or determination of the IRB).

8.4.2 ADVERSE EVENT MANAGEMENT

Subjects entered onto this protocol will only be subject to limited blood sampling. There will be expected events as a result of these procedures. The only AEs that will be recorded on this protocol will be those related to phlebotomy, except for the expected events, as described below.

Expected Events

The following are mild (Grade 1) to moderate (Grade 2) signs or symptoms that are induced by or associated with phlebotomy. If deemed related to phlebotomy by the PI, they will **not** be recorded as AEs in the Research Electronic Data Capture (REDCap) system per protocol, unless deemed by the PI to be abnormal or greater than Grade 2.

- Bleeding or bruising at venipuncture site

Reactions should be graded in the following manner:

Grade 1	Mild transient reaction; interruption not indicated; intervention not indicated.
Grade 2	Interruption indicated but responds promptly to symptomatic treatment (e.g., nonsteroidal anti-inflammatory drugs, narcotics, intravenous fluids); prophylactic medications indicated for less than 24 hours.
Grade 3	Prolonged (e.g., not rapidly responsive to symptomatic medication and/or brief interruption of infusion); recurrence of symptoms following initial improvement; hospitalization indicated for clinical sequelae.
Grade 4	Life-threatening consequences; urgent intervention indicated.
Grade 5	Death.

Information on AEs related to research procedures developing after the procedure will be collected by the investigators and entered into a computerized database (REDCap, Section 10.1.6).

Table 1. Attribution of Adverse Events (AEs)

Relationship	Attribution	Description
Unrelated intervention	Unrelated	The AE is clearly NOT related to the intervention
	Unlikely	The AE is doubtfully related to the intervention
Related intervention	Possibly	The AE may be related to the intervention
	Probably	The AE is likely related to the intervention
	Definitely	The AE is clearly related to the intervention

8.4.3 REPORTING

The PI is responsible for reporting per NIH IRB and NECHR reporting requirements. Reportable events will be tracked and submitted to the NIH IRB and NECHR as outlined in NIH Human Research Protections Program Policy 801.

According to Policy 801, all UPs, major protocol deviations, all non-compliance, new information that might affect the willingness of a subject to enroll or remain in the study, and any suspension or termination of research activity will be reported within 7 calendar days of investigator awareness. Any death of a research subject that is possibly, probably, or definitely related to the research will be reported within 24 hours of investigator awareness.

The following events will be reported to the NIH IRB and NECHR in summary at the time of continuing review:

- AEs and SAEs that are not UPs, as a narrative summary indicating whether these events were within the expected range.
- Minor and major protocol deviations.
- UPs reported to the NIH IRB/NECHR.
- Non-compliance reported to the NIH IRB/NECHR that is not related to a protocol deviation.

The PI will report UPs, major protocol deviations, and deaths to the NIAID clinical director according to institutional timelines.

9 STATISTICAL CONSIDERATIONS

9.1 STATISTICAL HYPOTHESES

We hypothesize that seroprevalence as measured via ZIKV PRNT50 titers will be lower in Cambodian human adults and macaques compared to Thai human adults and macaques.

9.2 SAMPLE SIZE JUSTIFICATION AND ANALYSIS PLAN

Though we will also be assessing DENV and CHIKV in humans and monkeys, the following statistical plan is primarily guided by the anticipated ZIKV seroprevalence for two reasons. First, DENV has hyperendemic transmission in both Thailand and Cambodia. Therefore, we expect that sample sizes that are adequate for ZIKV will also be adequate for dengue. Second, CHIKV is known to have sporadic and highly focal transmission in both countries, but there is not enough information to develop reasonable assumptions about the expected prevalence. All sites in Thailand and Cambodia have had documented ZIKV transmission in the past.^{3,18}

As there are limited data available for the seroprevalence of these arboviruses in macaques in Southeast Asia, we based our assumptions about seroprevalence on a field study in Senegal that identified seroprevalence of CHIKV in three species of monkeys.¹⁹ This study found that the seroprevalence across all three species was high, 72% (479/667). There are no studies evaluating ZIKV seroprevalence in macaques in Southeast Asia, only scattered reports from Malaysia, Brazil, and Africa that focused detection on active viremia, though an African study noted 16% seroprevalence of ZIKV.^{6,20,21} Preliminary analyses from our Thai collaborators show that an initial screen for pan-flavivirus antibodies in the Thai macaques is nearly 100% positive ([name], Mahidol University, personal communication). Treating sampled macaques as mutually independent simple random samples of binary responses for seropositivity to a given arbovirus, a sample of 100 monkeys per site will yield an average 95% confidence interval (CI) width of less than or equal to 0.2 for seroprevalence at each site, and we will have 80% power to detect a 25% relative reduction in seroprevalence relative to a site where seroprevalence is 75% using a binomial test of proportions with a Type-1 error rate of 0.05.

With regards to the sample size in humans, Thailand and Cambodia have both been endemic for dengue for many years. Only recently has ZIKV been actively detected in both countries.^{18,22-24} In Thailand, a serosurvey in a sample of 21 humans estimated ZIKV seroprevalence to be 76% (95% CI: 52%, 91%).²⁵ Another survey of 600 migrant workers from four Southeast Asian countries, 150 of whom were from Thailand, estimated overall seroprevalence to be 38.8% and seroprevalence among the Thai cohort to be 50.7%.²⁶ However, in Cambodia, the estimated seroprevalence was lower, estimated to be <1% definitively with 37.3% equivocal results.⁸ These equivocal results were based on a potentially cross-reactive IgM assay and indicated a recent flavivirus infection with either Japanese encephalitis virus (JEV), DENV, or ZIKV. Treating sampled humans as mutually independent simple random samples of binary responses for seropositivity, a sample of 300 humans in Cambodia will yield an average 95% CI width of less than or equal to 0.052 for presumed seroprevalence centered at 0.05 (Figure 2).

Our secondary objective is to compare human ZIKV seroprevalence in Cambodia with ZIKV seroprevalence in Thailand. Conservatively taking a value of 50% seroprevalence for ZIKV in Thailand and 37% seroprevalence in Cambodia, we calculate that a sample size of N=300 Cambodian participants and N=300 Thai participants will be sufficient to attain 90% power to reject a null hypothesis of no difference in seroprevalence using a binomial test of proportions with a Type-1 error rate of 0.05.

[figure not shown]

Figure 2. Expected precision of seroprevalence estimate versus sample size and true seroprevalence

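### Does the 80% macaque power, set at a 75% reference rate borrowed from a chikungunya survey, misstate the power for the Zika hypothesis?

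*Combined protocol and SAP*

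**What the plan says.** Section 9.1 has one statistical hypothesis, that "seroprevalence as measured via ZIKV PRNT50 titers will be lower in Cambodian human adults and macaques compared to Thai human adults and macaques". Section 9.2 opens by saying that "the following statistical plan is primarily guided by the anticipated ZIKV seroprevalence". It sets chikungunya aside as a basis for planning because "there is not enough information to develop reasonable assumptions about the expected prevalence".

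For macaques, section 9.2 then says that "we based our assumptions about seroprevalence on a field study in Senegal that identified seroprevalence of CHIKV in three species of monkeys", with 72% (479/667) positive. It adds two facts about Zika in primates: "There are no studies evaluating ZIKV seroprevalence in macaques in Southeast Asia", and "an African study noted 16% seroprevalence of ZIKV". It also reports that almost all Thai macaques were positive on a first screen for flavivirus antibodies in general. The power statement follows: 100 animals per site, for any one arbovirus, give "80% power to detect a 25% relative reduction in seroprevalence relative to a site where seroprevalence is 75" per cent, by a binomial test of proportions at a type 1 error rate of 0.05. The expected 95% confidence interval width per site is at most 0.2.

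The human part of section 9.2 cites Thai Zika figures of 76% (21 people) and "seroprevalence among the Thai cohort to be 50.7" per cent (150 people). It powers the human comparison at 50% against 37%. Section 9.3.2 plans a two-sample test of proportions between countries and, separately, Wilcoxon rank sum tests on PRNT50 titers, including Thai against Cambodian macaques.

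**The concern.** The plan claims to be led by Zika and says chikungunya cannot support prevalence assumptions, yet its macaque paragraph leans on a chikungunya survey. Power is given at one reference rate only. That rate is close to the top of the Thai human Zika figures and far above the single primate Zika figure cited.

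Power for a fixed relative reduction falls quickly as the reference rate falls, because the absolute difference shrinks with it. If Thai macaque Zika seroprevalence were 50% or lower, a 25% relative reduction would be missed more often than found. Someone who remembered only the 80% might then read a non-significant macaque test as evidence that the two countries do not differ.

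**Working it through.** **Inputs.** From section 9.2: n = 100 per site, reference rate 0.75, a 25% relative reduction (so 0.5625 at the other site), alpha 0.05. The plan does not say whether the test is one- or two-sided; two-sided reproduces its figure. Animals are treated as independent, as the plan does.

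**Formula.** For rates p1 and p2 with mean p̄, power = Φ{ [ |p1 − p2|·√n − 1.96·√(2p̄(1 − p̄)) ] / √( p1(1 − p1) + p2(1 − p2) ) }.

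**The plan's own figure.** p̄ = 0.65625.
- |p1 − p2|·√n = 0.1875 × 10 = 1.875
- 1.96 × √(2 × 0.65625 × 0.34375) = 1.96 × 0.6717 = 1.3165
- √(0.1875 + 0.2461) = 0.6585
- (1.875 − 1.3165)/0.6585 = 0.848, and Φ(0.848) = 0.802

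The stated 80% is reproduced. Exact enumeration of the same test gives 80.4%. A continuity-corrected or Fisher test would give 75.7%.

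**The same formula at other reference rates.** For example, at 50% against 37.5%: (1.25 − 1.96 × 0.7016)/0.6960 = −0.180, so power is 0.429. The last column is the rate at the other site that would give 80% power.

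| Reference rate | After 25% relative reduction | Power | Rate detectable with 80% power |
|---|---|---|---|
| 90% | 67.5% | 98% | 75% (17% relative fall) |
| 85% | 63.75% | 94% | not computed |
| 80% | 60% | 88% | not computed |
| 75% | 56.25% | 80% | 56% (25%) |
| 72% | 54% | 75% | 53% (26%) |
| 50.7% | 38.0% | 44% | 31% (38%) |
| 50% | 37.5% | 43% | 31% (39%) |
| 30% (illustrative) | 22.5% | 22% | 14% (54%) |
| 16% | 12% | 13% | 4% (74%) |

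Exact enumeration agrees: 44.4% at a 50% reference and 13.0% at 16%.

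**Larger contrasts with 100 per site.** 50% against 30% has 83% power, 16% against 2% has 94%, and 16% against 1% has 97%.

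**Precision.** The Wald interval for one site is widest at a rate of 0.5: 2 × 1.96 × √(0.25/100) = 0.196. The statement that the width is at most 0.2 therefore holds at every rate.

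**The case for a change.** The strongest case for a change compares the plan with itself. For humans it takes 50% against 37% as a conservative Zika contrast, a relative reduction of 13/50 = 26%. That is almost the reduction used for macaques, but from a much lower reference. Put those human rates on 100 macaques per site and power is about 46%, not 80%. The near-universal positive screen in Thai macaques does not rescue the 75%: it was not specific to Zika, and section 9.2 itself calls dengue hyperendemic in both countries. Section 9.3.2 names a test but no confidence interval for the difference, and the remedy would cost only a few lines.

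What stands is that the 80% has not been shown for Zika and depends heavily on the reference rate. Four things limit its force:

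- The sentence carries its own condition, a site at 75%, and refers to any one arbovirus. It does not attribute 80% power to Zika.
- The uncertainty is disclosed alongside it: no regional macaque data, and the 16% African figure.
- Rates above 75% are as open as rates below it, and there power is higher, 88% to 98% over references of 80% to 90%. Listing only the lower rates would be one-sided. A 16% to 12% contrast is also one that the plan never proposes for macaques.
- Nothing in sections 9.1 to 9.3.2 says that a non-significant test will be taken to mean no difference.

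**Conclusion.** The concern describes the basis of the assumption correctly but identifies no error. The 80% is right for the contrast stated (80.2%), the precision statement is right (at most 0.196), and the condition on the reference rate is written into the sentence. What is absent is a sensitivity range, and supplying one would leave the number of animals, the test and the estimate as they are. According to the Statement of Compliance, Thai macaque sampling was done in 2018, so a revised power figure could not have altered that side of the comparison.

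The Thai-Cambodian contrast is a secondary objective. The primary macaque aim is to estimate seroprevalence in Cambodian macaques and compare it with humans, and its per-site precision does not depend on the 75%. The planned Wilcoxon comparison of macaque titers also means that the binary test is not the only evidence between countries.

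A competent analyst would report the macaque difference with its 95% interval. Under a 25% relative reduction the half-width is about 12.9 percentage points at a 75% reference and 13.6 at 50%, which shows directly what a non-significant result can exclude. No change is needed. This rests on 100 independent animals per site and a two-sided 0.05 test, and on the Thai macaque Zika rate being unknown, as the plan says.

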9.3 STATISTICAL ANALYSIS

9.3.1 ANALYSIS OF THE PRIMARY ENDPOINT

The primary endpoint will be defined as:

- Assessment of seroprevalence via screening ELISA and/or PRNT50 titers for ZIKV, DENV, and CHIKV in Cambodian adults.
- Assessment of seroprevalence via screening ELISA and/or PRNT50 titers for ZIKV, DENV, and CHIKV in Cambodian macaques as compared to humans.

PRNT50 titer is a continuous variable (e.g., 0 to 40960) as measured from human and macaque sera at a single timepoint. For the purpose of classifying an individual as positive for a particular arbovirus, a PRNT50 titer of 50 will be taken to indicate that an individual has seroconverted (based on distribution of assay, we can consider <10 as seronegative, 10-50 as indeterminate, and >50 as seroconverted). We will estimate seroprevalence rates for humans and macaques, and report summary statistics of seroprevalence and titer distributions overall and within meaningful subgroups (e.g., males vs. females, by decade of age, by occupation, by bed net use, by intensity of self-reported interaction and duration with macaques).

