3 OBJECTIVES AND ENDPOINTS

OBJECTIVES	ENDPOINTS	JUSTIFICATION FOR ENDPOINTS
Primary		
Describe the seroprevalence of ZIKV, DENV, and CHIKV in humans living in close proximity to long-tailed macaques in Thailand and Cambodia.	Assessment of seroprevalence via screening ELISA and/or PRNT50 titers for ZIKV, DENV, and CHIKV in Cambodian adults.	PRNT assays are the gold standard to detect virus-specific antibodies given multiple circulating flaviviruses in Southeast Asia. Understanding the prevalence of these Aedes -transmitted viruses, and how they differ across the Mekong region, is critical to understanding the risk to Cambodians of future epidemics.
Compare the serology patterns against ZIKV, DENV, and CHIKV between NHPs and humans living in the same areas.	Assessment of seroprevalence via screening ELISA and/or PRNT50 titers for ZIKV, DENV, and CHIKV in Cambodian macaques as compared to humans.	Because primates can be amplifying hosts of these viruses, it is critical to understand the prevalence of these Aedes -transmitted viruses in macaques as well.

OBJECTIVES	ENDPOINTS	JUSTIFICATION FOR ENDPOINTS
Secondary		
Compare serology patterns against ZIKV, DENV, and CHIKV in macaques and humans between Thailand and Cambodia.	Comparative assessment of seroprevalence via PRNT50 titers for ZIKV, DENV, and CHIKV in Cambodian adults and macaques to that of Thai adults and macaques.	Understanding how the prevalence of these Aedes -transmitted viruses differs across the Mekong region is critical for cross-border disease detection and management, particularly given the high level of human migration in the Greater Mekong Subregion.
Compare serology patterns against Aedes aegypti salivary gland homogenate proteins in humans and monkeys between Thailand and Cambodia.	Assessment of reactivity to salivary gland homogenate of Aedes aegypti as detected by ELISA or western blot in human and macaque sera.	Characterizing vector salivary protein reactivity profiles (mosquitos, ticks, fleas) in Cambodians with vector-borne disease is the first step to better understanding transmission patterns, responsible vectors, and Cambodians' risk of exposure to these vectors.

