8.3 LABORATORY EVALUATIONS

Specific laboratory methods for each assay and instructions for handling and storage of samples will be maintained in a manual of procedures (MOP) that includes all the standard operating procedures (SOPs) for the study.

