8.3.1 SPECIMEN COLLECTION, PREPARATION, HANDLING, AND SHIPPING

All human and NHP biological samples will be received, processed, aliquoted, and stored at the central laboratories of CNM-NIH or Kampong Speu District Referral Hospital according to standard lab procedures.

Given that the purpose of the protocol is to build research capacity in Thailand and Cambodia, CNM-NIH lab personnel may travel between labs with de-identified samples to learn how to optimally prepare their samples in order to bring that knowledge and training back to Cambodia. Similarly, if cross-reactivity is determined to be a problem in the PRNT assays, certain exploratory assays (e.g., blockade of binding or BOB assays) may be carried out in one lab and not the other, necessitating transport of de-identified samples between labs. Samples requiring transport from the clinical collection site to the designated central repository or to the main NIH labs in the US will follow designated study sample shipping procedures, which will include shipment of samples with no participant identifiers.

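### Section 9.3.1 calls a serum ZIKV-positive from its ZIKV PRNT50 titre alone; without reference to the same serum's DENV titre, dengue cross-neutralisation could inflate ZIKV seroprevalence and distort the Thai–Cambodian comparison

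*Combined protocol and SAP*

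**What the plan says.** Section 9.3.1 sets the rule on each virus's own titre: for "classifying an individual as positive for a particular arbovirus, a PRNT50 titer of 50 will be taken to indicate that an individual has seroconverted". It adds bands in parentheses: "we can consider <10 as seronegative, 10-50 as indeterminate, and >50 as seroconverted". Section 9.3.2 then compares seroprevalence between countries by a two-sample binomial test, and titres by Wilcoxon tests. Neither section compares ZIKV with DENV titres in one serum, provides a class for flavivirus reactivity that cannot be assigned to a virus, or allows for misclassification.

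Other sections bear on this:

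- Section 9.2: "DENV has hyperendemic transmission in both Thailand and Cambodia".
- Section 8.3.1 makes one provision for PRNT: "if cross-reactivity is determined to be a problem in the PRNT assays, certain exploratory assays" may be run, possibly in one laboratory and not the other. It gives no trigger and no link to the positivity rule.
- Section 3 justifies the assay: "PRNT assays are the gold standard to detect virus-specific antibodies given multiple circulating flaviviruses in Southeast Asia".
- Section 8.3 places laboratory detail elsewhere: "Specific laboratory methods for each assay and instructions for handling and storage of samples will be maintained in a manual of procedures". That manual is not among the documents.
- Section 9.1 states the only formal hypothesis: "seroprevalence as measured via ZIKV PRNT50 titers will be lower in Cambodian human adults and macaques compared to Thai human adults and macaques".

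**The concern.** If dengue antibody can push a ZIKV PRNT50 above 50, the rule counts that serum as ZIKV-positive. The indeterminate band keeps low titres out of the positives but does nothing about cross-reactive titres above the cutoff.

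Two results are exposed. The primary ZIKV estimate would be too high, and a larger sample would not correct it. In the country comparison, equal cross-reactivity shrinks a true difference, while unequal cross-reactivity can create, hide or exaggerate one. The Wilcoxon comparisons offer no independent check, because they use the same ZIKV titres.

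**Working it through.** **Inputs from Section 9.2.** 300 humans per country; planning prevalences of 50% (Thailand) and 37% (Cambodia); type 1 error 0.05; presumed Cambodian prevalence 0.05 with an average 95% CI width of at most 0.052.

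**Assumed.** c is the share of truly ZIKV-negative sera whose ZIKV PRNT50 exceeds the cutoff through dengue antibody. Sensitivity is taken as 1. The documents give no value for c, so ranges are shown.

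**The plan's own figure.** A two-sided pooled z test of 0.50 versus 0.37 with 300 per country has power 0.897 (0.901 by exact enumeration). The stated 90% reproduces, and it assumes error-free classification.

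**1. Level.** Apparent prevalence = p + (1 − p)c. With p = 0.05:

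- c = 0.02: 0.05 + 0.95 × 0.02 = 0.069
- c = 0.05: 0.05 + 0.95 × 0.05 = 0.0975
- c = 0.10: 0.05 + 0.95 × 0.10 = 0.145

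The bias, 0.95c, exceeds half the planned CI width (0.052 / 2 = 0.026) once c > 0.026 / 0.95 = 0.027.

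**2. Equal c in both countries, true 50% versus 37%.** The apparent difference is 0.13 × (1 − c).

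| c | Thailand | Cambodia | Difference | Power |
|---|---|---|---|---|
| 0 | 0.500 | 0.370 | 0.130 | 0.90 |
| 0.05 | 0.525 | 0.4015 | 0.1235 | 0.86 |
| 0.10 | 0.550 | 0.433 | 0.117 | 0.82 |
| 0.20 | 0.600 | 0.496 | 0.104 | 0.73 |

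**3. Unequal c, no true difference, 300 versus 300.** Rejection rate of the nominal 5% test (normal approximation):

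| True prevalence in both | c = 10% vs 15% | c = 10% vs 12% |
|---|---|---|
| 50% | 0.095 (apparent 0.550 vs 0.575) | 0.057 |
| 37% | 0.121 (0.433 vs 0.4645) | 0.061 |
| 5% | 0.342 (0.145 vs 0.1925) | 0.099 |

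Exact enumeration agrees to within 0.01.

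**4. Cost of a paired-titre rule.** If such a rule retains a share s of true positives in both countries and there is no cross-reactivity, the test compares 0.50s with 0.37s:

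- s = 0.9: 0.450 vs 0.333, power 0.84
- s = 0.8: 0.400 vs 0.296, power 0.76
- s = 0.6: 0.300 vs 0.222, power 0.59
- s = 0.5: 0.250 vs 0.185, power 0.49

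Simulating a real 50% versus 37% difference with no cross-reactivity, the result is significant under the single cutoff but not under the paired rule in about 8% of studies at s = 0.9 and 15% at s = 0.8. Contrasting significance under the two definitions would therefore sometimes flag a real effect as an artefact.

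**5. Wording at the cutoff.** A titre of exactly 50 counts as seroconverted in the first clause of the rule and as indeterminate in the bands. Section 9.3.1 does not say whether sera at 10–50 stay in the denominator. If 5% of sera exceed 50 and an assumed 5%, 10% or 20% lie at 10–50, dropping the latter gives 0.05/0.95 = 5.3%, 0.05/0.90 = 5.6% or 0.05/0.80 = 6.3%, against 5% if they are kept.

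**The case against.** The strongest reply is that the documents do not show a PRNT problem. Section 3 presents PRNT as the virus-specific assay, and Section 8.3.1 speaks of cross-reactivity only conditionally. A reader might take the 37.3% equivocal Cambodian results in Section 9.2 as evidence against the rule. They are not: "These equivocal results were based on a potentially cross-reactive IgM assay", whereas this study's endpoint is IgG (Section 2.2) and its classifier is PRNT50. That history is background only. This part of the reply stands. The documents support *could bias*, not *is biased*.

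Second, the size is assumed. A reader might seize on the 34% rejection rate. It needs 5% true prevalence in both countries, but Section 9.2 presumes 5% for Cambodia only and plans on 50% for Thailand. This stands too.

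Third, the manual of procedures may already contain a paired-titre rule, in which case the gap is a missing cross-reference. That cannot be excluded. Still, the positivity rule is set in Section 9.3.1, which cites no such rule.

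Fourth, Section 8.3.1 does foresee the problem and names follow-up assays. They are optional and exploratory, however, and as written cannot change how a serum is classified.

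Finally, a paired-titre rule discards some true ZIKV infections, and the ELISA and/or PRNT50 wording of the primary endpoint means that some sera may have no DENV PRNT50. Both points are fair and shape the fix.

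**Conclusion.** The point holds as a gap in the endpoint definition. Followed as written, the plan uses no DENV information when it calls a serum ZIKV-positive, in a setting that it describes as hyperendemic for dengue and with an assay that it allows may cross-react. The 90% power calculation is not in error; it simply assumes perfect classification.

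The size is unknown. Under assumed rates, a c of 2–10% would turn a true 5% into 6.9–14.5%, and an equal c of 5–20% would cost about 4 to 17 percentage points of power at the planning values. With no true difference, a 10% versus 15% split gives about 9% to 12% rejection at true prevalences of 50% or 37%. The 34% figure is an extreme case and should not be the headline. The documents do not support a claim that the ZIKV results will be wrong, or that PRNT is known to cross-react here.

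The change should be made before titres are compared, because a rule chosen afterwards would be data-driven. The exact-50 overlap and the 10–50 denominator are separate, minor wording points and add no weight to this one.

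**What to change.** **1. Section 9.3.1, sensitivity analysis.** Keep the single-cutoff analysis as primary. Pre-specify a second classification in which a serum is ZIKV-positive only if its ZIKV PRNT50 is above the cutoff and exceeds its highest measured DENV PRNT50 by a stated multiple. Fix the multiple before titres are compared, name the DENV serotypes run, and apply the rule identically in both countries. Class all other ZIKV-reactive sera, including those without a DENV PRNT50, as *flavivirus, not attributable*, and report their number by country. If the manual of procedures already holds such a rule, cite it instead.

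Report the prevalence difference with its 95% CI under both definitions. Compare the estimates, not whether each is significant.

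*Cost.* SAP wording and one extra analysis, using titres already planned where both were run. Additional serotypes, or DENV PRNT50 on sera that would otherwise lack it, would mean more assays. The paired rule loses true ZIKV infections in people with high DENV titres (power about 0.84, 0.76, 0.59 or 0.49 at an assumed 90%, 80%, 60% or 50% retention). It may itself be affected if DENV titres differ by country, and it does not address JEV. For these reasons it should remain a sensitivity analysis.

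**2. Section 9.3.1, wording.** Choose one cutoff, either ≥50 or >50, and state that sera at 10–50 that are not positive under it count as not positive and stay in the denominator. This costs one sentence.
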